2. SYNOPSIS

Please state why this study is not considered a Clinical Trial of an Investigative Medicinal Product
	
This study is not a Clinical Trial of an Investigative Medicinal Product as we are not investigating the efficacy of atorvastatin but using it as a pharmacological tool to understand the role of inflammation in emotional and reward processing.
 
This study does not fit the MHRA definition of a clinical trial as one designed to: discover or verify/compare a drug's clinical effects; to discover or verify/compare its pharmacological effects (e.g. pharmacodynamics); to identify or verify/compare its adverse reactions; or to study its absorption, distribution, metabolism or excretion (https://www.gov.uk/government/uploads/system/uploads/attachment_data/file/317952/Algothrim.pdf).
	

List all sites where study will be conducted
	
Neurosciences Building, Department of Psychiatry, University of Oxford, Warneford Hospital, [name]
	

Age Range of Study Participants
	
18-50 years old
	

Planned Sample Size
	
50 healthy volunteers (25 per group)
	

Planned Study Duration (n.b. A minimum approval period of 1 year and maximum of 5 years can be granted)
	
24 months
	

Anticipated Start Date
	
1st February 2019
	

Anticipated End Date
	
1st February 2021
	
	
Objectives
	
Outcome Measures

Primary
	
To investigate the effects of seven-day atorvastatin administration on emotional processing
	
Accuracy and reaction times on computer-based tasks of emotional processing (e.g. facial expression recognition, emotional categorisation and memory), comparing those receiving drug and placebo.

Secondary
	
To investigate the effects of seven-day atorvastatin administration on reward processing
	
Accuracy and reaction times on computer-based tasks of reward processing comparing those receiving drug and placebo.

	To investigate the effects of seven-day atorvastatin administration on inflammation	Changes in high sensitivity-C Reactive Protein (hs-CRP) from baseline to seven-day, comparing those receiving drug and placebo
Name of drug/substance	Atorvastatin	
Purpose of drug/substance use in this study	
Work in our group has revealed that short-term (7-day) administration of antidepressants produces positive biases in the processing of emotional information in healthy volunteers. Such effect might be an important neuropsychological mechanism of antidepressant action.
 
The current study will investigate the effect of seven-day administration of atorvastatin 20mg on emotional and reward processing tasks in healthy volunteers. There is evidence that statins may exert antidepressant effects via anti-inflammatory and anti-oxidant pathways, and it is therefore predicted that atorvastatin will have positive effects on emotional and reward processing.
	
Adverse reactions and side effects posing a particular risk with this treatment	
Muscle pain or weakness: usually mild and quickly responding to stopping or switching medication
 
Elevation of liver transaminases: significant only in case of pre-existing hepatic disease
 
Rhabdomyolysis: very rare but severe myopathy associated with elevated creatine kinase and myoglobinuria
 
Nasopharyngitis, epistaxis, pharyngo-laryngeal pain: usually mild and quickly responding to stopping or switching medication
 
Headache: usually mild and quickly responding to stopping or switching medication
 
Gastrointestinal disturbances (constipation, diarrhoea, flatulence, dyspepsia, nausea): usually mild and quickly responding to stopping or switching medication
 
New-onset diabetes mellitus: in predisposed individual with pre-existing hyperglycaemia
 
Haemorrhagic stroke: in patients with prior haemorrhagic stroke or lacunar infarct
	

3. ABBREVIATIONS

BMI	Body Mass Index
CTRG	Clinical Trials & Research Governance, University of Oxford
CUREC	Central University Research Ethics Committee
DSM-5	Diagnostic and Statistical Manual of Mental Disorders-5
ETB	Emotional Test Battery
GP	General Practitioner
hs-CRP	high sensitivity-C Reactive Protein

MS IDREC	Medical Sciences Inter-Divisional Research Ethics Committee
PIL	Probabilistic Instrumental Learning
SCID-5	Structured Clinical Interview for DSM-5
SOP	Standard Operating Procedure

4. BACKGROUND AND RATIONALE

Depression is common and associated with considerable health disability (Kassebaum-2016). Traditional antidepressants mainly work by modulating monoamine levels in the synaptic cleft (Harmer-2017); however, the evidence that depression is caused by impaired serotonin or noradrenaline activity is weak and inconsistent (Cowen-2015), and indeed current antidepressant strategies remain burdened by partial efficacy, poor side-effects profile, and a slow onset of therapeutic action (Penn-2012). Therefore, there is a pressing need to develop antidepressant medications with novel non-monoaminergic mechanisms of action (Jha-2018) – or, conversely, to identify alternative pathophysiological pathways leading to depression that can be targeted with new drugs. Intriguingly, there is growing evidence that both peripheral and central inflammation play a role in the pathophysiology of depression (Miller-2017).

Patients with depression consistently show negative biases in emotional processing, which are believed to play a key role in the aetiology and maintenance of their clinical symptoms (Roiser-2013). Overall, robust evidence suggests that early changes in emotional processing can serve as valid surrogate markers of antidepressant efficacy (Harmer-2017); for example, seven days' treatment with selective serotonin and noradrenaline reuptake inhibitors (citalopram and reboxetine respectively) compared to placebo decreases the recognition of negative facial expressions and recall of negative versus positive stimuli in healthy volunteers (Harmer-2004). Conversely, another study using the pro-inflammatory cytokine interferon- α showed that inflammatory-mediated depression can be associated with an increased recognition of negative facial expressions (Cooper-2017). Furthermore, depression associated with inflammation is characterised by significant symptoms of anhedonia (Miller-2017), which has been linked to diminished neural responses to reward anticipation (Felger-2017). Such reward-deficit is particularly refractory to conventional serotonergic and noradrenergic antidepressants (McCabe-201), and even the antidepressant bupropion (a noradrenaline and dopamine reuptake inhibitor), whilst inducing positive changes in emotional processing, appears to worsen reward processing (Walsh-2018). However, the reversal of this deficit in reward processing is still considered as a valuable marker of target engagement for anti-inflammatory drugs in depression, as a more sensitive outcome measure than traditional rating scales designed to capture the global clinical symptomatology (Miller-2017).

The 3-hydroxy-3-methylglutaryl-CoA reductase inhibitors or statins are recommended and have been widely used since the '80s for the primary and secondary prevention of cardiovascular diseases (NICE 2014). It is now established that these medications have significant anti-inflammatory effects that are independent from their lipid-lowering properties (Jain-2005), as well as appearing early in treatment only after seven day of administration (Macin-2011). Statins are considered extremely safe drugs: their more common side-effect are muscle pain or weakness (usually mild and quickly responding to stopping or switching medication) and elevation of liver transaminases (significant only in case of pre-existing hepatic disease), whereas more serious adverse events include rhabdomyolysis (very rare but severe myopathy associated with elevated creatine kinase and myoglobinuria), new-onset diabetes mellitus (in predisposed individual with pre-existing hyperglycaemia), and haemorrhagic stroke (in patients with prior haemorrhagic stroke or lacunar infarct); however, clinical trials have ultimately concluded that such adverse events attributed to statin therapy in routine practice are not actually

caused by it (Collins-2016), especially at doses lower than 80mg/day and when used for less than 52 weeks (Li-2016). Other common ($\geq 1/100$, $< 1/10$) but usually mild side-effects include: nasopharyngitis, pharyngo-laryngeal pain, epistaxis, headache, and gastrointestinal disturbances (constipation, diarrhoea, flatulence, dyspepsia, nausea). Importantly, a potential antidepressant effect for statins has been confirmed in animals (Kilic-2012), as well as clinically in observational (Parsaik-2014) and interventional studies (Salagre-2016). Although their anti-inflammatory and anti-oxidant properties have been involved, the mechanisms underlying the antidepressant effects of statins remain unclear, therefore further translational studies have been advocated in order to elucidate this aspect (Köhler-Forsberg-2017).

In this exploratory study, we will investigate the effect of seven-day administration of atorvastatin 20mg once daily compared to placebo on emotional and reward processing tasks in 50 healthy volunteers. In view of the previous evidence that statins may exert antidepressant effects via anti-inflammatory and anti-oxidant pathways, we predict that atorvastatin will have positive effect on emotional and reward processing.

5. PARTICIPANTS

Description of Study Participants
50 healthy volunteers aged 18-50 years
Inclusion Criteria

 • Male or female • Aged 18-50 years • Sufficiently fluent English to understand and complete the tasks • Body Mass Index in the range of 18-30 • Participant is willing and able to give informed consent for participation in the study • Not currently taking any regular medications (except the contraceptive pill)
Exclusion criteria

The participant may not enter the study if any of the following apply:
 
 • Currently any regular medications (except the contraceptive pill) • History or current significant psychiatric illness • Current alcohol or substance misuse disorder • History or current significant hepatic disease • History or current significant neurological condition (e.g. epilepsy) • Known hypersensitivity to the study drug (i.e. atorvastatin) • Pregnant, breast feeding, women of child-bearing potential not using appropriate contraceptive measures • Participation in a study that uses the same or similar computer tasks as those used in the present study • Participation in a study that involves the use of a medication within the last three months
Recruitment

Participants will be recruited by word of mouth, emails to departmental mailing lists (sent by who usually has access to those mailing lists on our behalf), and posters located in University Departments. Moreover, we will use adverts (APPENDIX A: STUDY ADVERTS) sent to Junior Common Rooms and Middle Common Rooms, displayed in Colleges and University departments and local community buildings through existing participant registries at the Department of Psychiatry and the Department of Experimental Psychology. Participants will also be recruited via advertisement through Oxford Brookes, following approval from Oxford Brookes University Research Ethics Committee. The following additional statement will be inserted into any recruitment documents for Oxford Brookes students and/or staff: "Oxford Brookes University has knowledge of this study and has permitted recruitment at the University. In the event of any questions about the study, please contact the researchers in the first instance. Should you need to contact anyone at Oxford Brookes about this further, please email: [contact]. Adverts will also be placed on local information websites (e.g. Daily Info, Oxford University Gazette), newspapers, local magazines, on the radio, and on the lab webpage, Facebook page, and Twitter account. The adverts will contain brief information about the inclusion criteria for the study, as well as contact details for the named researchers.

After a potential volunteer has contacted the research team, they will be sent the Participant Information Sheet via email. We will also send the Participant Information Sheet via email (APPENDIX B: RECONTACT EMAIL TEMPLATE) to participants from previous studies who gave consent to be approached about possible participation in future research studies they may be suitable for. The participant will be given as much time as they need to decide whether they would like to take part and will be invited to ask any questions that they have about the study. If the participant decides that they do not want to take part in the study, they will be thanked for their interest and there will be no further contact from the research team. If the participant decides they would like to take part, they will be invited for a screening visit at the Neurosciences Building, Warneford Hospital. At the beginning of this visit, one of the named researchers will explain the study to the participant and answer any questions that they have. The researcher will then take written consent from the participant. All of the named researchers have been trained in taking informed consent.

Screening and Eligibility Assessment

Informed Consent will be obtained at the start of the screening, prior to the administration of questionnaires or the Structured Clinical Interview for DSM-5 disorders.

A maximum of four weeks will be allowed between screening and randomisation to atorvastatin or placebo. If this duration is exceeded, another screening will need to be performed to ensure eligibility.

At screening, information about demographics, medical history, concomitant medication, and psychiatric history (using Structured Clinical Interview for DSM-5) will be taken (APPENDIX C: SCREENING FORM). Female participants will also have a urine pregnancy test.

Information Provided to Participants and Informed Consent

The Participant Information Sheet (APPENDIX D: PARTICIPANT INFORMATION SHEET) will be presented to the participants, in written as well as in verbal form. Both will detail the exact practical demands of the study, written from the participant's perspective, in lay language (the nature of the study, what it will involve for the participants, the implications and constraints of the protocol, the known side-effects and any risks involved in taking part, what will happen to the data collected). It will be clearly stated that the participant is free to withdraw from the study at any time for any reason and with no obligation to give the reason for withdrawal. The participant will be allowed as much time as they wish to consider the information, and the opportunity to question the Investigator, their GP, or other independent parties to decide whether they will participate in the study.

The participant must personally sign and date the latest approved version of the Informed Consent Form (APPENDIX E: INFORMED CONSENT FORM) before any study specific procedures are performed. Written

informed consent will then be obtained by means of participant dated signature and dated signature of the person who presented and obtained the informed consent. The person who obtained the consent will be suitably qualified and experienced and have been authorised to do so by the Principal Investigator. A copy of the signed Informed Consent Form will be given to the participant. The original signed form will be retained at the study site.

Participant Confidentiality

The study staff will ensure that the participants' data are safeguarded. The study will comply with the Data Protection Act, which requires personal data to be anonymised as soon as it is practical to do so. Where possible, participants will be identified only by a participant ID number on study documents and on any electronic database. Documents (such as consent forms) that contain identifying data and/or information allowing this to be linked to the participant ID will be stored separately under strict access controls. All documents will be stored securely and only accessible by study staff and authorised personnel.

It will be made clear to the participant that information shared within the course of the screening and study visits may be shared within the research team but will not be shared with anyone else. The exceptions to this are stated clearly in the Participant Information Sheet: "Information collected about you during the course of the research will be kept confidential. Confidentiality would be breached only in the very rare circumstance that it was judged that you or someone else was at immediate risk of serious harm. In these circumstances only, information necessary to ensure immediate safety would be released. The only other circumstance in which information would be released is if it was requested by an order of a court of law".

6. STUDY PROCEDURES

Baseline Assessments and Procedures

Individuals who are interested in participating in the study will be invited to attend a Screening Visit (maximum 2 hours) at the Neurosciences Building, Warneford Hospital.

Demographic information will be collected:

- Age (years, months), years in full-time education

Participants' eligibility to take part will be checked by recording the following:

- Weight, height, and BMI
- Medical history (including family psychiatric history), details of current and past medication
- Current and prior use of drugs (to exclude for drug use in the three months prior to the study)
- Menstrual cycle (in order to avoid scheduling testing in the premenstrual week)
- SCID-5 interview (Structured Clinical Interview for DSM-5) to probe for current or past psychiatric illness
- Urine pregnancy test (female participants only)

The following baseline assessments will be completed (APPENDIX F: QUESTIONNAIRES):

- Beck Depression Inventory (BDI)
- Eysenck Personality Questionnaire (EPQ)

- Positive and Negative Affect Schedule (PANAS)
- Side-effects questionnaire (to determine baseline of bodily symptoms/'side-effects')
- Snaith-Hamilton Pleasure Scale (SHAPS)
- State and Trait Anxiety Inventory (STAI)
- Visual Analogue Scales (VAS) measuring subjective state

Also, phlebotomy will be undertaken to obtain a sample of:

- high sensitivity-C Reactive Protein

Participants will be asked to wait while their eligibility to take part is assessed by a medical doctor involved in the study (maximum 30 minutes). Any participant for whom additional information is required before an eligibility judgment can be made will be asked to return on a different day once this information has been obtained.

Eligible participants will be randomised to receive either 7-day atorvastatin 20mg (25 participants), or 7-day placebo (25 participants) administration. Randomisation will occur on the day of screening, or up to a maximum of 4 weeks after screening. Randomisation after the Screening Visit will occur in the event that further information is needed before determining whether participants are eligible to take part (for example, if a participant needs to follow-up with details of allergies, or previous studies they have taken part in). In this case, if more than 4 weeks have elapsed, another Screening Visit will be performed to ensure participants are still eligible. The randomisation code will be drawn up by a researcher not involved in the study using an online randomisation tool (<https://www.sealedenvelope.com/simple-randomiser/v1/lists>). Randomised participants will be given 7 days of the drug to take home, as well as full instructions of how and when to take them.

The atorvastatin drug and the placebo will be provided by the Oxford Pharmacy Stores and will be encapsulated at the Neurosciences Building according to previously agreed standard operating procedures (APPENDIX G: Neurosciences, SOP Number: Encapsulation Version 2: 22.10.2012). Blinding will be achieved by the identical matching of the atorvastatin and placebo treatments. Participants will not be aware of the treatment that they will be receiving; neither will the researcher, as this study is double-blind.

Allocation of treatments will be recorded on a Randomisation List, which will be updated when each new participant enters the randomised phase. The list will be held at the Neurosciences Building by a scientist uninvolved in the study.

The study medication and placebo will be stored in a secure environment at the Neurosciences Building accessible only to staff. It will be stored at room temperature and accounted for using agreed study documentation. Using the Randomisation List and the participant's unique randomisation code, staff will determine whether to dispense active or placebo tablets.

The randomisation code will be broken if a participant requires treatment for a new medical condition or experiences serious adverse reactions and either of these situations make it clinically important to know what medication they are taking. A 24/7 emergency mobile contact number will be provided on a wallet-sized card given to participants during their Research Visit. The research team member on-call will be able to contact the medical supervisor and they will make the decision to unblind. In order to unblind the participant, the medic will access the list kept in a secure cabinet at the Neurosciences Building and will disclose the allocation within a maximum of one hour. If breaking the code is necessary, only the individual's code will be broken. Data from unblinded participants will not be admitted to analysis. If unblinding occurs, the researcher will record the reason and result of the unblinding, as well as the date and time of the event.

During the week of drug/placebo administration, participants will be advised not to drink alcohol and not to carry out activities requiring full alertness, such as driving, if they are aware of any impairment. During this week, a researcher will phone up the participant on day 2 and day 4 to check that there are no concerns. Additionally,

participants will receive a text message every day reminding them to take the study medication. They will have the 24-hour contact phone number of a member of the study team and be encouraged to get in contact if they have any concerns or queries during the study week, or if their medication or health status changes.

Subsequent Visits

The Research Visit (approximately 2 hours) will take place after day 7 of atorvastatin/placebo administration. This visit will involve administration of behavioural tasks measuring emotional and reward processing. It will take place at the Neurosciences Building, Warneford Hospital.

Participants will complete the following questionnaires before the behavioural tasks:

- Positive and Negative Affect Schedule (PANAS)
- Side-effects questionnaire
- State Anxiety Inventory (state-STAI)
- Visual Analogue Scales (VAS)

Also, phlebotomy will be repeated to obtain a sample of:

- high sensitivity-C Reactive Protein

The behavioural tasks will include the Oxford Emotional Test Battery (ETB), which has previously been found to be sensitive to the effects of antidepressants, and a reward task of Probabilistic Instrumental Learning (PIL). The ETB involves the presentation of emotion-related words and pictures of faces with different expressions. The reward task involves repeatedly choosing between two options and there is the possibility of winning up to £10 depending on the choices made (see 'Expenses and Benefits' below). All stimuli will be presented on a computer screen and participants will be required to respond via button presses on a keyboard.

Participants will be asked to report their adherence to the 7-day administration of atorvastatin/placebo.

At the end of the research visit, a member of the study team will ask participants to try to guess which treatment they received, as a measure of how successful the blinding was.

Sample Handling

Blood samples (4mL = i.e. 1 teaspoon) taken during the Screening Visit and the Research Visit for investigating hs-CRP will be handled at the Neurosciences Building's laboratory. On the same day, they will be rendered acellular by centrifugation on receipt and stored at -30°C until assay. Any excess material remaining at the end of the study will be disposed of by the laboratory within 6 months according to the Human Tissue Authority guidelines. The samples will be stored in a freezer at the Neurosciences Building in an anonymised form. Access to the samples will be by the research team and the samples will be in the custody of [name] who will hold the key code linking the samples to a particular individual. The samples will be analysed for once all participants have completed the study.

Female participants will be required to give a urine sample for a pregnancy test at the Screening Visit. Urine samples will be destroyed immediately after the test result has been obtained.

Discontinuation/Withdrawal of Participants from Study

Each participant has the right to withdraw from the study at any time. In addition, the Investigator may discontinue a participant from the study at any time if the Investigator considers it necessary for any reason including:

- Pregnancy

- Ineligibility (either arising during the study or retrospectively having been overlooked at screening)
- Significant protocol deviation
- Significant non-compliance with treatment regimen or study requirements
- Withdrawal of Informed Consent
- Loss to follow up

If a participant is withdrawn, no further procedures or observations will continue to be required. Withdrawal from the study will result in exclusion of the data for that participant from the analysis. Withdrawn participants will be replaced. The reason for withdrawal, if given, will be recorded in the Participant Log of the Research Master File.

Definition of End of Study

The end of the study for participant involvement is the date of the last visit of the final participant.

Expenses and Benefits

Participants will be paid £100 upon completion of their participation in the research. In addition, they may win up to £10 depending on the choices they make in the reward task (see 'Subsequent Visits' above). If they do not complete the study, they will be given a pro-rata amount to recompense the time they did spend in the study. Reasonable travel expenses for any visits will be reimbursed on production of receipts, or a mileage allowance provided as appropriate.

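### Baseline hs-CRP and the repeated state scales are taken at screening, so for participants whose randomisation is deferred the baseline can be up to about five weeks old at follow-up, with a possible, avoidable loss of precision in secondary comparisons

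*Combined protocol and SAP*

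**What the plan says.** Section 6 (Baseline Assessments and Procedures) lists PANAS, the side-effects questionnaire, STAI, VAS and an hs-CRP blood sample among the Screening Visit procedures. Under Subsequent Visits, PANAS, side-effects, state-STAI, VAS and hs-CRP are repeated at the Research Visit, after day 7 of dosing. Sample Handling confirms that blood is "taken during the Screening Visit and the Research Visit for investigating hs-CRP"; no third sample is planned.

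On timing, section 5 says "A maximum of four weeks will be allowed between screening and randomisation to atorvastatin or placebo", and section 6 agrees: "Randomisation will occur on the day of screening, or up to a maximum of 4 weeks after screening". Delay is conditional: "Randomisation after the Screening Visit will occur in the event that further information is needed before determining whether participants are eligible to take part". Participants in that position "will be asked to return on a different day once this information has been obtained". Beyond the limit, "if more than 4 weeks have elapsed, another Screening Visit will be performed to ensure participants are still eligible".

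The synopsis gives the second secondary outcome as "Changes in high sensitivity-C Reactive Protein (hs-CRP) from baseline to seven-day, comparing those receiving drug and placebo". Section 9 analyses mood, anxiety, side-effects and hs-CRP by repeated measures ANOVA. On the assay, Sample Handling says: "The samples will be analysed for once all participants have completed the study".

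**The concern.** A baseline helps a comparison of change only as far as it correlates with the follow-up value. For someone randomised on the day of screening, the two measurements are about a week apart. For someone deferred to the limit they are about five weeks apart, and four of those weeks are untreated. hs-CRP and state mood can drift in that time. If they do, the older baseline adds noise to the change score in a study with 25 per group.

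For hs-CRP the early draw also serves no purpose that the plan states. The samples are assayed only after everyone has finished, so the result cannot inform eligibility. hs-CRP is the only direct measure of inflammation in the study, and inflammation is the mechanism that the synopsis sets out to probe, so avoidable noise in it is worth removing if that is cheap.

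**Working it through.** **The plan's own power figure.** The only one is 0.9 for accuracy on fearful faces (section 9), from means 10.64 and 3.36 and SDs 9.77 and 5.96. The difference is 7.28, the SD is √((9.77² + 5.96²)/2) = 8.09, and d = 0.90. With 25 per group and two-sided 5% (assumed; the plan does not state alpha), the normal approximation gives Φ(0.90 × √12.5 − 1.96) = 0.889, and the t distribution gives 0.876. So 0.9 is reproduced to rounding. It concerns a task given only at the Research Visit, with no baseline, so nothing below alters it.

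**Interval.** Same-day randomisation: about 7 days. Longest permitted deferral: 28 + 7 = 35 days. Both assume that dosing starts at randomisation and that the Research Visit follows promptly after day 7.

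**Precision of change.** With two time points, the group-by-time test in a repeated measures ANOVA is the t-test on change. Section 9 also says that all data will be analysed by between-groups ANOVA; applied to change scores, that is the same test. With equal variance σ² at both visits, Var(change) = 2σ²(1 − r).

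Let r₁ be the correlation over about one week, r₂ the correlation over about five weeks, and f the share deferred. Relative to a current baseline for everyone:

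variance ratio = [(1 − f)(1 − r₁) + f(1 − r₂)] / (1 − r₁), and SE ratio = its square root.

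Example with r₁ = 0.8, r₂ = 0.7, f = 0.25: (0.75 × 0.2 + 0.25 × 0.3)/0.2 = 1.125, and √1.125 = 1.061.

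The documents give none of r₁, r₂ or f, so the values in the table are assumptions. Each row also puts every deferred participant at the full four weeks, which overstates the loss if most wait less.

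| r₁ to r₂ | SE, 10% deferred | SE, 25% deferred | SE, 50% deferred |
|---|---|---|---|
| no fall | 0 | 0 | 0 |
| 0.7 to 0.6 | +1.7% | +4.1% | +8.0% |
| 0.8 to 0.7 | +2.5% | +6.1% | +11.8% |
| 0.7 to 0.5 | +3.3% | +8.0% | +15.5% |
| 0.8 to 0.6 | +4.9% | +11.8% | +22.5% |

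**In terms of power.** Suppose a change comparison had 80% power with a current baseline for everyone. With 25% deferred and r falling from 0.8 to 0.7, the effective size is 25/1.125 = 22.2 per group and power is Φ(2.802/1.061 − 1.960) = 75%. With r falling from 0.8 to 0.6, the effective size is 25/1.25 = 20.0 and power is 71%. With 10% deferred, the two powers are 78% and 76%. With no fall, power stays at 80%.

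**The case against.** The best defence is that the effect may be negligible. Same-day randomisation is the first route named, deferral needs a specific cause such as missing allergy details, and re-screening caps the gap. No document shows that the correlation falls between one and five weeks. All of this stands, and it is why the loss can be stated only as a range that includes zero.

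A reader might go further than the documents allow in three ways.

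- That the comparison is biased. It is not: the gap arises before allocation and is independent of arm.
- That the stated outcome goes unmeasured in deferred participants. The wording can be read with seven-day naming the follow-up time point, and section 6 places baseline at screening. On that reading the outcome is measured as defined for everyone; what may be stale is its starting value.
- That the study loses its stated power. The primary tasks have no baseline, and the state scales are not named outcomes in the synopsis or section 9.

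A practical objection also stands. Section 8c lists STAI, PANAS, side-effects and VAS in the baseline screening, has a doctor review the screening before inclusion, and has mood questionnaires reviewed for signs of distress. Moving these scales until after eligibility is settled would take them out of that review. The argument for moving a measurement therefore holds for hs-CRP only.

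Finally, adjusting for baseline by ANCOVA would help without moving anything: its variance is σ²(1 − r²), against 2σ²(1 − r) for change, so 0.51σ² against 0.60σ² at r = 0.7. That recovers part of the loss, but it does not make an old baseline current: if r is 0.8 with a current baseline, even the change score has variance 0.40σ².

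**Conclusion.** The point holds as a minor one about design. The baseline is tied to screening, dosing may start up to four weeks later, and no repeat is planned, so for a deferred subset of unknown size the interval can reach about 35 days. The consequence is limited to possible loss of precision for hs-CRP and the repeated state scales. With up to a quarter of participants deferred, the increase in standard error runs from nil to about 12% over the assumed correlations; at half deferred it could reach about 22%. These sizes rest on assumed correlations, equal variances at the two visits and the full four-week wait for everyone deferred. The reason to act is that the remedy costs almost nothing, not that the loss is shown to be large.

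**What to change.** - Define baseline hs-CRP as a single sample taken after eligibility is confirmed, on the day capsules are dispensed and before the first dose. Same-day participants have it later in the same visit, since section 6 allows at most 30 minutes for the eligibility decision. Deferred participants have it at the return visit that they already make. This takes dispensing to happen at that visit; section 6 does not say so outright, but section 7 has capsules dispensed in the same building.
- Keep all questionnaires at screening. For deferred participants only, repeat PANAS, state-STAI, VAS and side-effects on the dispensing day and use the repeat as baseline. BDI, EPQ, SHAPS and trait anxiety need no repeat.
- Record the baseline-to-follow-up interval, and state that the dispensing-day measurement is the baseline after a re-screen too, where the plan now mentions only eligibility.

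Cost: protocol wording, a reordered visit checklist and the amendment approval described in section 12. There is no extra draw or visit. Deferred participants have a slightly longer return visit and a few minutes of repeated questionnaires; volunteers found ineligible are spared a blood draw.
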